### 9.2.2 Time to Cessation of O2 Support

Among subjects requiring supplemental oxygen therapy at the time of enrollment with baseline room air oxygen saturation of  $\leq 92\%$ , time to cessation of O2 support will be analyzed using a Cox proportional hazards model where cessation of O2 support is defined as the finding of stable SpO2 at two consecutive room air SpO2 values that are separated by at least 8 hours greater than 92%. In the event that a subject has only one room air SpO2 measurement but has been stable off oxygen (for instance as an outpatient), the second value may be a carry forward of the prior measurement. Time from onset of symptoms to VIS410 treatment and the number of doses of oseltamivir (Tamiflu) prior to VIS410 treatment for the current case of influenza will be included as covariates in the analysis. P-values (using the Wald statistic) for each VIS410 dose versus placebo, VIS410 total versus placebo and VIS410 4000 mg versus 2000 mg will be presented.

### 9.2.3 Time to Clinical Response

Time to clinical response (days) is defined as time to the finding of normality (as defined below) for 4 out of 5 vital signs that will be determined upon physical examination. Clinical response is defined as:

- Afebrile with core temperature  $\leq 37.8^{\circ}\text{C}$ , without use of antipyretics (oral  $\leq 37.2^{\circ}\text{C}$ )
- Respiratory rate  $\leq 24$  beats per minute
- Oxygen saturation  $\geq 95\%$  on room air without support or a return to pre-infection status, if pre-infection status was  $< 95\%$
- Pulse rate  $\leq 100/\text{min}$
- SBP  $\geq 90$  mm/Hg, without vasopressor use

For determination of time to clinical response, achievement of any of the criteria above will carry forward to missing data at subsequent visits. Subjects who do not experience clinical response will be censored at the last available vital sign visit date. Time to Clinical response will be analyzed using Kaplan-Meier techniques.

Pre-infection oxygen saturation data on room air status was not collected on the CRF. Therefore, prior to database lock, for any subject with persistent oxygen saturation on room air  $< 95\%$ , a query to the investigator will be sent to request historic oxygen saturation on room air data. If a baseline oxygen saturation on room air value collected during 6 months prior to enrollment is available, the information will be captured and recorded in a spreadsheet maintained by data management at POI. This spreadsheet will be reviewed, signed and locked prior to database lock. This information will be used to define pre-infection oxygen saturation on room air for the purposes of calculating time to clinical response. If there are no available medical record data and oxygen saturation remains below 95% on room air, the subject will be analyzed as not experiencing clinical response.

Note, the number of vital signs abnormalities (utilizing the above criteria) may range from 0 to 5 for subjects enrolled in the trial, although the expectation is that all subjects will have at least one abnormality. Therefore, this analysis will be conducted in two ways. First, the probability of time to clinical response (defined as the finding of at least 4 of 5 normal vital signs using the criteria above) will be calculated via Kaplan-Meier; under this analysis, some subjects will have met criteria for a clinical response at baseline. Time to clinical response will be calculated as Date of

January 17, 2019

Event – Date of Day 1. If the event was not achieved then the value will be censored and calculated as Date of the last available assessment – Date of Day 1. P-values for each VIS410 dose versus placebo, VIS401 total versus placebo and for VIS410 4000 mg versus 2000 mg will be presented. The number and percentage of subjects in each treatment group with clinical response will be summarized. Results will be presented graphically as well.

This analysis will be repeated for subjects with >2 vital signs abnormalities at baseline, using the same analysis algorithm described above; under this analysis, no subject will meet criteria for clinical response at baseline.

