6.3.3 Time to Cessation of Ventilator Support

Start and stop time for mechanical ventilation will be documented in EDC.

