10.2 Randomization and Blinding

An IWRS will be used to allocate the randomized treatments to subjects with stratification by presence or absence of positive pressure ventilation (PPV) at baseline. Pharmacists must obtain the status of the subject relative to PPV at baseline via query, and this data must be input into the IWRS prior to randomization. The randomized treatment assignment will be transferred electronically for integration with the clinical study data at the appropriate time.

PPV includes any respiratory assistance using a mechanical ventilation device and can be either invasive or noninvasive ventilation. Invasive PPV includes intubation with endotracheal tube with mechanical ventilation (most common) or tracheostomy with mechanical ventilation. Noninvasive PPV includes use of facemask, nasal plugs, or nasal mask with mechanical ventilation. The devices are named according to the type of mechanical ventilation given continuous positive airway pressure (CPAP) or bi-level positive airway pressure (BiPAP).

Randomization will be used to avoid bias in the assignment of subjects to treatment, to increase the likelihood that known and unknown subject attributes (eg, demographic and baseline characteristics) are evenly balanced across treatment arms.

The maintenance of the study blind is critical for an unbiased assessment of the safety and efficacy of the study drug. All study staff that evaluate subjects and render decisions regarding subject care will remain blinded to the study treatment each subject receives.

The designated study site pharmacist or designee will remain unblinded. Also, unblinded clinical research associates will handle study drug accountability.

The study will be conducted in a double-blind manner. The CRO, site study personnel, and Visterra personnel will not be aware of which treatment (VIS410 or placebo) the subjects have been given. Subjects will not be aware of which treatment they have been administered.

Subjects will be randomized 1:1:1 to receive VIS410 2000 mg, VIS410 4000 mg, or placebo over a 2-hour infusion with pretreatment regimen of PO or IV diphenhydramine 50 mg plus either ibuprofen 400 mg PO or acetylsalicylic acid 320-325 mg PO approximately 60 minutes before IV infusion of VIS410/placebo.

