  - Geographic region of enrollment
- Time to clinical response defined as resolution of at least 4 of 5 vital signs
  - Afebrile with core temperature ≤ 37.8°C, without use of antipyretics (oral ≤ 37.2°C)
  - Oxygen saturation ≥ 95% on room air without support or a return to pre-infection status, if pre-infection status was < 95%
  - Pulse rate ≤ 100/min
  - Systolic blood pressure ≥ 90 mm/Hg, without vasopressor use
  - Respiratory rate ≤ 24 beats per minute
- Clinical status ordinal scale mean area under curve for Days 1-7 and Days 1-14, using linear numeric scores for the ordinal categories.
- Comparison of clinical status ordinal scale scores for selected individual days (ie, Days 3, 4, 5, and 6)
- Comparison of clinical status ordinal scale scores using modified ordinal scale criteria (ie, pooling of selected severity criteria scores)
- Comparison of discrete ordinal scale parameters, including days of ventilator support, days in intensive care, and duration of hospitalization
- Number of days to resumption of usual activities
- All-cause and attributable mortality rates at Day 14, 28 and 56
- Total number of days in hospital and/or intensive care unit (ICU) from admission to discharge and rate of rehospitalization due to influenza A relapse/complication
- The incidence, severity, and duration of signs and symptoms of influenza-like illness as assessed by the FluPRO Questionnaire (see Appendix 16.3.1)
- The percentage of subjects with new bacterial pneumonia/superinfection

January 17, 2019

- The percentage of subjects with influenza-related complications
- VIS410 pharmacokinetic (PK) parameters in serum
- Titer of anti-VIS410 antibody positive samples
- Genotypic and/or phenotypic assessment to determine the emergence of VIS410 and oseltamivir-resistant viruses

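### The 4-of-5 clinical-response rule credits a respiratory rate controlled by a ventilator, so a ventilated subject can be counted as a responder

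*SAP*

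**What the plan says.** SAP 9.2.3 measures time to clinical response as "time to the finding of normality (as defined below) for 4 out of 5 vital signs". Any four of the five will do, the earliest assessment that meets the rule sets the date, and the response need not be sustained. Three of the five are protected against normality produced by treatment:

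- temperature: "without use of antipyretics"
- oxygen saturation: "on room air without support or a return to pre-infection status"
- systolic pressure: "without vasopressor use"

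Respiratory rate is given bare: "Respiratory rate ≤ 24 beats per minute". Pulse is also unconditioned. The same five criteria, with the same gap, stand in SAP 3.2 and in Protocol 3.2 and 10.6.3.

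SAP 9.2.3 adds three rules that bear on this point:

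- A criterion once achieved is carried forward into later missing data.
- If no historic saturation is on record and the subject's room-air saturation stays under 95%, the subject is a non-responder.
- The analysis is repeated, with the same algorithm, in subjects with more than 2 abnormal signs at baseline.

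Ventilated subjects are in the trial. Protocol 5.2.1 (criterion 4) admits any PPV, and Protocol 10.2 stratifies on it and explains that "PPV includes any respiratory assistance using a mechanical ventilation device and can be either invasive or noninvasive ventilation". The MITT definition in SAP 5.1.3 does not remove them. Ventilation times are collected: "Start and stop time for mechanical ventilation will be documented in EDC" (Protocol 6.3.3).

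**The concern.** The criteria follow a principle: a sign that is normal only because of support does not count. Respiratory rate departs from it, although in a respiratory-failure trial a device may be setting the rate. A subject in ICU on mechanical ventilation scores 6 on the ordinal scale, the worst non-fatal category (SAP 9.1). This endpoint can record the same subject on the same day as a success.

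Baseline PPV is stratified, so ventilation at entry should be roughly balanced across arms. Intubation after baseline is an outcome that treatment may change. If VIS410 prevented intubation, intubated placebo subjects could gain responses and the apparent benefit would shrink. An arm with more intubations could look better than it is. SAP 9.2.3 produces p-values for four comparisons on this endpoint, and the Efficacy section of the protocol synopsis uses p-values as one indicator of which endpoints are sensitive enough for Phase 3.

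**Working it through.** The plan gives no figure to reproduce here, so the check is a count of patterns under the rule.

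**Inputs.** There are five criteria, each met or not met, and response needs a count of 4 or more (SAP 9.2.3). Assumption: a ventilated subject fails the saturation criterion, because it requires room air without support. I read the return-to-pre-infection alternative as a room-air comparison too, since SAP 9.2.3 obtains the pre-infection value on room air.

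**All subjects.** Patterns: 2^5 = 32. Responder patterns: C(5,4) + C(5,5) = 5 + 1 = 6.

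**Saturation not met (ventilated).** Patterns: 2^4 = 16. Response needs all four remaining signs, so 1 of 16 qualifies: temperature, respiratory rate, pulse and systolic pressure all met.

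**Responses created by intubation.** Exactly one pattern turns from non-response to response when only the rate changes:

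| Sign (illustrative values) | Before intubation | After, set rate 18 |
|---|---|---|
| Temperature 37.0 °C oral, no antipyretic | met | met |
| Pulse 98 | met | met |
| Systolic pressure 105, no vasopressor | met | met |
| Respiratory rate | 32, not met | 18, met |
| Saturation on room air | not met | not met |
| Count | 3 of 5 | 4 of 5 |

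The response is dated to the first assessment after intubation.

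**Do other provisions close the gap?**

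- *More than 2 baseline abnormalities.* If the case above were the baseline state, it has two abnormalities and would be excluded from the repeat. A subject who starts with rate, saturation and, say, temperature abnormal (2 of 5 met) is included. After intubation, and once the fever settles without antipyretics, that subject reaches 4 of 5 on the ventilator. There are 2^3 − 1 = 7 such baseline patterns with rate, saturation and at least one other sign abnormal. The restriction governs entry to the analysis, not later support.
- *Persistent low room-air saturation.* This provision depends on a room-air value that remains below 95%. A ventilated subject may have no room-air reading. A subject who later recovers no longer has persistently low saturation, yet the response has already been dated to the ventilated assessment.
- *Complete clinical response.* SAP 16.6.1 and 16.6.3 list outputs with this name. Read as 5 of 5, it could not occur while saturation fails. SAP 9.2.3 does not define it, and it does not replace the 4-of-5 analysis.
- *Carry-forward.* This worsens the problem: a rate met on the ventilator counts as met at later assessments where it is missing.

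**With respiratory rate not credited on PPV.** Saturation and rate both fail, so the count is at most 3 of 5 and the responder patterns while ventilated fall from 1 to 0.

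**The case against.** The strongest reply is that the gap is narrow. The subject must, at one assessment, have temperature in range without antipyretics, pulse 100 or less, systolic pressure 90 or more without vasopressors, a rate the device controls, and no earlier response. PPV under Protocol 10.2 includes CPAP and BiPAP, where the rate may be the subject's own. The persistent-low-saturation provision is a real safeguard for some subjects, and the repeat analysis removes some others. The endpoint is secondary in a study that states it is not powered, and SAP 4.1 calls its p-values informational. The ordinal scale and time to ventilator cessation would show an intubation for what it is. All of this stands, and it limits the size of the problem. None of it supplies the missing condition.

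A reader might go further and infer a count of misclassified subjects. Assuming 5% to 30% of 40 per arm are on PPV gives 0.05 × 40 = 2 to 0.30 × 40 = 12 per arm. The documents do not support that as an error count. They give no PPV proportion, the range is pure assumption, and it counts subjects on PPV rather than those who also meet the other three criteria under a device-controlled rate.

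A reader might also infer that this endpoint's p-value alone decides the Phase 3 choice. The protocol synopsis sets p-values beside an assessment of each endpoint's contribution to patient benefit.

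**Conclusion.** The point holds as a gap in the definition of one secondary endpoint. Applied exactly, SAP 9.2.3 can count a ventilated subject as a clinical responder, and intubation after baseline can supply the fourth sign. The provision on saturation below 95% is only a partial safeguard.

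The size of any bias, and its direction in this trial, cannot be computed from the documents. The ceiling is the number of PPV subjects who also meet the temperature, pulse and systolic pressure criteria. The Day 7 ordinal primary endpoint is unaffected.

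The conclusion rests on two assumptions: that the ventilator sets or controls the recorded rate in the subjects concerned, and that the saturation criterion fails on a ventilator. The table shells are a separate document (SAP 16.7) and were not available; a rule there could narrow the gap. Because the correction is cheap, it is worth making.

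**What to change.** State in SAP 9.2.3 that a subject cannot be counted as a clinical responder at an assessment made during mechanical ventilation or PPV, and list this in SAP 16.1 as a change from the protocol analysis. Either of two rules achieves it:

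1. Treat respiratory rate as not met while the subject is on PPV, using the EDC start and stop times. The daily ordinal scale serves as a check, though its ventilation category covers ICU stays only. Confirm that the recorded times include noninvasive PPV.
2. Require the room-air saturation criterion as one of the four. This needs no merge of ventilation times, but it also applies to non-ventilated subjects on supplemental oxygen: responder patterns fall from 6 to 5 for everyone. Rule 1 is therefore the narrower change.

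Under either rule, do not carry forward a respiratory-rate criterion recorded on PPV.

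The cost of rule 1 is one clause and one merge of data already collected. Responses will be slightly fewer or later. Some spontaneous rates on CPAP will go uncredited, although those subjects fail the room-air saturation criterion in any case.

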³ Single nasopharyngeal swab will be obtained from one nostril for influenza A rapid test. This screening test is not necessary if the subject has a prior influenza A positive test by Rapid Antigen Test or with another commercially available test including PCR, FIA, or ELISA within the prior 48 hours of screening.
⁴ Collect all medications taken, including over-the-counter, within 7 days prior to VIS410/placebo administration.
⁵ Randomization will be stratified by presence or absence of positive pressure ventilation (PPV) at baseline to ensure an even distribution across treatment arms.
⁶ Subject diary will be provided upon discharge from the hospital and will record daily oseltamivir dosing (as applicable) and will have a daily VAS for assessing resumption of usual activities until either the subject reports that all usual activities (prior to influenza onset) can be performed or Day 56, whichever comes first. In addition, the Influenza Patient Reported Outcomes (FluPRO) Questionnaire will be provided and completed daily up until Day 14 (if applicable).
⁷ Additional safety assessments may be performed outside of the defined protocol criteria, at the Investigator's discretion.
⁸ Single 12-lead ECG will be performed after a 5-minute rest in supine position.
⁹ To be repeated only if screening and baseline visits are more than 24 hours apart.

-
- ¹⁰ Vital signs should be measured after 5 minutes of rest in a supine position and include heart rate, respiratory rate, and blood pressure. During hospitalization, vital signs will be measured at the end of the infusion on Day 1 and then BID (preferably at the same time each day) up until Day 14 or discharge from the hospital if this occurs prior to Day 14.
- ¹¹ Baseline SpO₂ on room air to be documented, if available. Once randomized, SpO₂ to be measured using pulse oximetry 3 times daily (approximately every 8 hours) at approximately the same time each day until stable. Stable SpO₂ is defined as two consecutive SpO₂ values of > 92% on room air that are at least 8 hours apart.
- ¹² During hospitalization, body temperature will be recorded at the end of infusion on Day 1 then BID up until Day 14 or discharge from the hospital if discharge occurs prior to Day 14. In cases where obtaining oral temperature is not possible, core temperature will be obtained. While hospitalized, the maximum temperature should be recorded for each 12-hour interval (from 12 AM to 12 PM and from 12 PM to 12 AM).

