6.3 Procedures for Sample and Data Collection

6.3.1 SpO₂ Oxygen Support

Baseline SpO₂ on room air to be documented, if available. Once randomized, SpO₂ will be measured using pulse oximetry 3 times per day (approximately every 8 hours) at approximately the same time each day until stable according to Table 1. Stable SpO₂ is defined as two consecutive SpO₂ values of > 92% on room air that are at least 8 hours apart.

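### SAP 9.2.3 carries an achieved SpO2 criterion into later missing values without checking oxygen use, which in a narrow case gives a false or early clinical response

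*SAP*

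**What the plan says.** SAP 9.2.3 sets five criteria: temperature, respiratory rate, oxygen saturation, pulse and systolic pressure. Response is "defined as the finding of at least 4 of 5 normal vital signs using the criteria above". The oxygen criterion is a saturation of at least 95% "on room air without support or a return to pre-infection status" where that status was itself below 95%.

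For gaps, the section states that "achievement of any of the criteria above will carry forward to missing data at subsequent visits". This departs from SAP 4.2, where missing values generally stay missing. The rule has no time limit and does not mention oxygen use.

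Footnote 11 to protocol Table 1, repeated in SAP 16.2, has SpO2 "measured using pulse oximetry 3 times daily (approximately every 8 hours) at approximately the same time each day until stable". Stable means two consecutive "values of > 92% on room air that are at least 8 hours apart". Protocol 6.3.1 agrees. No text says that readings restart if oxygen is resumed.

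The other signs continue. Footnote 10 reads "During hospitalization, vital signs will be measured at the end of the infusion on Day 1 and then BID", up to Day 14 or discharge, and covers heart rate, respiratory rate and blood pressure. Footnote 12 does the same for temperature.

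SAP 9.2.2 has its own carry-forward of a room-air reading, but restricts it to a subject who "has only one room air SpO2 measurement but has been stable off oxygen".

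**The concern.** The value being filled in is a claim about breathing room air without support. For a subject who is back on oxygen that claim is false, yet the carry-forward rule as written can still score it as met. The schedule makes this possible because SpO2 may go unrecorded after stability while the other four signs are still collected.

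Where the carried SpO2 supplies the fourth normal sign, a subject who has relapsed onto oxygen gets a response date. On that day the ordinal scale may show hospitalization with supplemental oxygen. Time to clinical response is tested for four treatment comparisons, and protocol 10.1 intends the p-values to help choose Phase 3 endpoints, so its event dates should be right.

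There is a second, related gap. The rule carries an achievement, not the latest status. Read literally, a sign that was achieved, then observed to fail, then missing would be scored as achieved.

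**Working it through.** The plan states no figure on this point, so there is none to reproduce. The check traces the rule and counts outcomes.

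**Worked case (invented values, rule applied as written)**

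| Day | SpO2 | Temperature | Pulse | Resp. rate | SBP | Normal signs |
|---|---|---|---|---|---|---|
| 2 | 96% on room air, twice, 8 h apart; scheduled readings end | 38.5 °C | 115 | 28 | normal | 2 of 5 |
| 3 | back on oxygen, none recorded | | | | | |
| 4 | on oxygen, none recorded | normal | normal | 28 | normal | 3 observed; 4 with SpO2 carried |

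On Day 4 the rule declares a response. With the room-air criterion counted as not met, it does not.

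**Count of patterns.** Let k be the number of the other four signs that are normal, for a subject on oxygen with SpO2 missing but achieved earlier.

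- SpO2 not met: response needs k ≥ 4, which is C(4,4) = 1 of 2^4 = 16 patterns.
- SpO2 carried as met: response needs k + 1 ≥ 4, so k ≥ 3, which is C(4,3) + C(4,4) = 4 + 1 = 5 of 16 patterns.
- Difference: 4 patterns, all with k = 3.

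**Illustration.** Assume each of the four signs is normal with probability p, independently. This is an assumption; the documents give no such values. The chance of being called a responder at one assessment is p^4 with SpO2 not met, and p^4 + 4p^3(1−p) with SpO2 carried.

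| p | SpO2 not met | SpO2 carried | Difference, 4p^3(1−p) |
|---|---|---|---|
| 0.60 | 0.1296 | 0.4752 | 0.3456 |
| 0.70 | 0.2401 | 0.6517 | 0.4116 |
| 0.80 | 0.4096 | 0.8192 | 0.4096 |
| 0.90 | 0.6561 | 0.9477 | 0.2916 |
| 0.95 | 0.8145 | 0.9860 | 0.1715 |

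These are conditional on a subject already in the exposed state. They are not rates for the trial.

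**What must coincide for the result to change**

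1. A room-air SpO2 of at least 95%, or the pre-infection level, was recorded. Scheduled readings can end at 93–94%, which leaves nothing to carry.
2. Response had not been reached before oxygen was resumed. A response already reached stands, since no sustained response is required.
3. Oxygen was resumed.
4. No later SpO2 was recorded.
5. Exactly three of the other four signs are normal.

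**Existing safeguard.** The one SpO2 exception in SAP 9.2.3 classes a subject as a non-responder when room-air saturation stays below 95% and no historic value is available. It does not address a missing value in a subject on oxygen.

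**The case against.** The strongest reply is that a subject known to be on oxygen has an observed failure of the without-support part of the criterion, not a missing value, so carry-forward never applies. The daily ordinal scale and the planned oxygen-support listing record that status. This is a sensible way to program it, but SAP 9.2.3 does not say so and does not bring those records into the algorithm. A literal application fills the gap.

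It can also be said that SpO2 is not necessarily missing after stability. The SpO2 row of the schedule has a mark in the last column, possibly a span to Day 56, and nothing forbids readings once oxygen restarts. That narrows the problem without removing it, since footnote 11 requires readings only until stability.

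The comparison with SAP 9.2.2 is limited. That rule supplies a second reading to define stability, and the two sections need not match. It does show that an off-oxygen condition can be written in a few words.

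Two stronger readings are tempting and not supported.

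- A reader might infer that carry-forward is why a subject on oxygen can be a responder. Mostly it is not: four of five already allows this when the other four signs are all normal, unless the exception for saturation below 95% is read as making SpO2 mandatory.
- A reader might infer that missing data can only push subjects toward response. A missing sign with no earlier achievement is not filled and cannot count as normal, so it can delay response.

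**Conclusion.** The point stands as a minor defect in a stated rule. SAP 9.2.3 can score the room-air criterion as met for a subject whose records show oxygen support, and where exactly three other signs are normal this produces a false or early response date.

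Its size in the trial cannot be computed, because the documents give no rate of return to oxygen. Since all five conditions must hold together, it is probably small. One might multiply guesses, such as 5–10% resuming oxygen by 20–40% with exactly three other signs normal, to get 1–4%. Neither input comes from the documents, and the product leaves out the requirements that response was not already reached and that a reading of at least 95% existed. It should not be quoted as an estimate.

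Nor do the documents show that the error favours one arm. The rule is the same in all arms of a blinded trial, and any bias would require the arms to differ in return to oxygen. The endpoint is secondary, and SAP 4.1 treats all p-values as informational.

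The conclusion rests on reading the carry-forward sentence literally and on SpO2 not being recorded after oxygen is resumed.

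**What to change.** Amend the carry-forward sentence in SAP 9.2.3 as follows.

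- When SpO2 is missing, carry an earlier achievement forward only if the oxygen-support records show no supplemental oxygen or ventilation at that assessment. Otherwise count the criterion as not met.
- Use the daily ordinal score as a cross-check to Day 14, not as the deciding record. It gives the worst status of the day, its score 5 (ICU without mechanical ventilation) does not show whether oxygen was in use, and it ends at Day 14 although vital-sign visits run to Day 56.
- Observed room-air readings always take precedence, including those taken later on the day of weaning.
- For all five signs, carry the last observed status rather than any past achievement, so that achieved, failed, missing is not scored as achieved.

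This leaves the four-of-five definition unchanged. A subject on oxygen with the other four signs all normal would be classified as now.

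The cost is a short SAP edit and a merge with oxygen-support and ordinal data already collected. No new assessments are needed.
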